Aim 2a: To obtain preliminary data on caregiver intermediate (self-efficacy for (a) coping with cancer and (b) abbreviated progressive muscle relaxation) and outcome variables (burden, psychological distress, quality of life) in intervention caregivers and waitlist control caregivers at the start of radiation (T1), end of radiation (T2), and 6-weeks post-radiation (T3).

Aim 2b: To compare intermediate (self-efficacy for (a) coping with cancer and (b) abbreviated progressive muscle relaxation) and outcome variables (burden, psychological distress, quality of life) between intervention caregivers and waitlist control caregivers at T1, T2, and T3.

Hypothesis: (Aim 2a) *Intermediate and outcome variables will improve in intervention caregivers post-intervention compared to pre-intervention and (Aim 2b) intervention caregivers will have better intermediate (higher self-efficacy for a) coping with cancer, and b) abbreviated progressive muscle relaxation) and outcome variables (less burden, less psychological distress, higher QOL) at T2 compared to waitlist control caregivers.*

Aim 3: To obtain preliminary data on caregiver cortisol response (cortisol slope, cortisol awakening response, area under the curve, and intra-individual cortisol variability) at T1 – T3 in intervention caregivers and waitlist control caregivers.

Hypothesis: *Intervention caregivers will demonstrate a more normal (steeper) diurnal cortisol rhythm (slope) at T2 compared to waitlist control caregivers.*

Aim 4: To refine intervention procedures and materials for future studies by examining: a) qualitative data from caregivers and interventionist notes and b) quantitative data regarding module utilization.

Methods and Measures

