Design: Recruitment will include both patients and caregivers, although patients are not receiving the intervention. We will recruit 40 caregivers (20 intervention caregivers; 20 waitlist control caregivers) of patients with head and neck cancer (HNC) referred for radiotherapy (RT) and their informal caregivers, before or at the start of patient RT. After baseline assessment, caregivers will be randomized at the time of registration using a randomization scheme uploaded into the registration system. The randomization scheme will be developed by the statistician. Block sizes will be chosen randomly to ensure that future assignments cannot be inferred from previous ones. Caregivers will be randomized to receive either a psycho-educational and stress management skills building intervention offered in a SSM format, accessible in hard copy and online, with iPads linking to study materials available during daily patient RT sessions, or a waitlist control group. Caregivers will complete assessments at the start of RT (T1), end of RT (T2), and 6-weeks post-RT (T3). Waitlist control caregivers will be offered *Prepare to Care* materials (without support from the study interventionist) after final assessment at T3. Patient participation is optional and restricted to providing consent for study staff to abstract information on clinical information from their medical record. If a patient declines to participate in the study, caregivers will be asked to report the patient clinical information collected at T1. See Appendix A for study schema.

Setting: Participants will be recruited from the outpatient radiation clinics at the Comprehensive Cancer Center of Wake Forest University and the Lexington Medical Center or by mail. Participants will meet with the study interventionist at the radiation clinic or by telephone, and have the option to access intervention materials from the study website using i-Pads that remain at the clinic or accessing the website away from the clinic. The self-management intervention is designed so that caregivers can utilize the kit in a preferred location (e.g., at home) and time.

Subjects selection criteria

Caregivers

- **Inclusion Criteria**

(1) providing the majority of the informal (unpaid) care during RT for a patient meeting inclusion criteria (see below) and participating in study, and (2) ≥ 18 years of age.

- **Exclusion Criteria**

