The first two modules provide cancer education and a list of supportive resources; modules 3-8 focus on stress management skills to enhance caregiver coping during RT (Table 1). Each module includes an introduction and rationale for the topic, strategies to overcome relevant challenges, and a weekly exercise. PMR training (in module 8) teaches caregivers to identify muscle tension signals and to use the signals as cues to trigger a relaxation response [45]. The breadth of topics and succinct modules are intended to provide a balance between addressing a comprehensive set of challenges and preventing participant burden.

Table 1. Prepare to Care Kit Components	
Module: Topic	Description
DVD Introduction	Brief introduction to the intervention: rationale and how to use the kit
Educational	
1: Cancer Education	Information about HNC, RT (+/- chemotherapy), side effects, and managing patient side effects
2: Using Your Resources	Information linking caregivers to supportive resources available within a) the CCCWFU, b) Forsyth County, and c) the internet
Stress Management Skills	
3: Managing Time	Managing a busy schedule, including recognizing competing outside demands & prioritizing
4: Seeking/ Accepting Support	Importance of social support, learning to identify supporters and ask for help when needed;
5: Communicating with Others	Strategies to optimize communication with provider, patient, and other friends/family members
6: Healthy Behaviors	Importance of healthy behaviors (diet, physical activity, sleep) as a cancer caregiver
7: Positive Coping	Learning to identify and re-frame negative thoughts[46]
8: Muscle Relaxation	Importance of engaging in relaxation; Also includes a CD with audio instructions for PMR

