Salivary Cortisol: Caregiver participants who do not have an endocrine disorder (e.g., diabetes and thyroid disorders), and are not currently taking a steroid-based medication are eligible for the saliva portion of the study. Materials for saliva collection will be mailed or distributed to eligible participants in person at the start of the study. Participants will collect saliva samples three times a day (at awakening, 30 minutes post-awakening, and bedtime) for two consecutive days following T1, T2, and T3. Saliva samples are collected by placing a cotton roll under the tongue for approximately 1-2 minutes which is subsequently stored in a plastic tube and refrigerated. Participants will be instructed to refrain from eating, drinking, smoking, brushing their teeth, using mouthwash, or engaging in exercise or similar physical activity for 30 minutes prior to saliva collection. Participants will be provided with saliva collection diaries to record compliance to these behaviors as well as the time in which their saliva samples were collected. After all six samples have been collected at each time point (T1, T2, T3), participants will return their samples in person at the radiation clinic (T1) or by mail (T2 & T3) using pre-paid postage to return their samples and saliva collection diaries to the Wake Forest study site. Once received at the study site, all samples will be immediately centrifuged to remove the saliva from the adsorbent swabs, discarding the swabs and swab holder. The collection tube containing the saliva will be weighed. The saliva will then be transferred in approximately equal aliquots to freezer storage tubes before freezing. All storage tubes will be labeled using a barcode. Sample aliquots will be stored in freezer boxes at -80° C until assayed. The location of each group of samples in the freezer will be recorded in the sample database.

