We will use a mixed effects model with a random subject effect and time (T1,T2,T3), group, and a group by time interaction to model change in the intermediate variables (self-efficacy for (a) coping with cancer (CI) and (b) PMR) and outcome variables (burden (CRA), depression (CESD), anxiety (PROMIS Short Form-Anxiety 7a), and QOL (CQoL-Canc), by group from T1 to T2 to T3). We will use linear contrasts to compare the intervention to the control group at T1, T2, and T3. In exploratory analyses we will model the relationship between each outcome and the intermediate variable, by including the intermediate variable as a fixed effect in the model. These results are exploratory due to concurrent measurement with outcome variables; in future studies we would capture potential mediators at an intermediate time point.

Aim 3: To obtain preliminary data on caregiver cortisol response (cortisol slope, cortisol awakening response, area under the curve, and intra-individual cortisol variability) at T1 – T3 in intervention caregivers and waitlist control caregivers.

Analysis Plan: Analyses for Aim 3 will be conducted using data from caregivers who were not excluded from the saliva portion of the study. Several summary measures will be derived from the three daily cortisol values, including the mean levels at each time, the mean cortisol awakening response (CAR – change in cortisol from awakening to 30 minutes), the area under the curve (AUC), the diurnal slope (change in cortisol between awakening and bedtime), and the intraindividual cortisol variability, which will be estimated using the methods as described in Sannes et al.[53] to assess group differences in cortisol parameters. We will use a mixed model to evaluate differences between the groups in these parameters at times T1 and T2 and T3. For a subset of the sample who completed measures on intermediate and outcome variables and cortisol, in exploratory models, we will include the cortisol summary measures as predictor variables in the models described for Aim 2 above.

Aim 4: To refine intervention procedures and materials for future studies by examining: a) qualitative data from caregivers and interventionist notes and b) quantitative data regarding module utilization.

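### Does Aim 3 need a cortisol slope defined per hour, rather than as the change from awakening to bedtime?

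*Combined protocol and SAP*

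**What the plan says.** The Aim 3 hypothesis under Objectives reads: "Intervention caregivers will demonstrate a more normal (steeper) diurnal cortisol rhythm (slope) at T2 compared to waitlist control caregivers". The Analytical Plan for Aim 3 lists the measures to be derived from the three daily cortisol values. Among them are the awakening response, explained as "change in cortisol from awakening to 30 minutes", and "the diurnal slope (change in cortisol between awakening and bedtime". A mixed model then compares the groups on these measures at T1, T2 and T3. A citation to a published method follows the last item in the list, intraindividual variability.

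The Salivary Cortisol section sets sampling at awakening, 30 minutes later and bedtime, "for two consecutive days following T1, T2, and T3". Diaries record adherence to the pre-sample restrictions "as well as the time in which their saliva samples were collected". No visible section says how those times enter the slope.

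On sequence, the Design section states: "After baseline assessment, caregivers will be randomized at the time of registration". Waitlist caregivers are offered the kit only once the last T3 assessment is done.

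**The concern.** A slope is normally a change per unit of time. For the awakening response a plain change is enough, because the interval is nominally 30 minutes for everyone. The interval from awakening to bedtime is not fixed. Two caregivers with the same hourly decline but different waking days get different difference scores.

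This would matter for the group comparison if the intervention altered waking-day length by T2. Module 6 in Table 1 covers "Importance of healthy behaviors (diet, physical activity, sleep) as a cancer caregiver", and only the intervention arm has it before T3. Part of an apparent cortisol effect could then reflect sleep schedule. An analyst could also compute both versions and report the more favourable one.

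A second worry concerns order. Saliva is collected on the days following T1 and T3. If allocation were disclosed before the T1 samples, or the kit handed to controls before the T3 samples, the T1 and T3 contrasts and change from T1 would be affected. The hypothesised T2 contrast would not be directly affected.

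**Working it through.** The plan gives no SD, effect size or power for the slope, so there is no stated figure to reproduce. The inputs below are assumptions, except the 20 per arm, which is the planned size.

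**1. Difference score when the hourly decline is constant.** Take a 16-hour waking day and an arm difference of 0.5 to 1 hour.
- 0.5/16 = 3.1%
- 1/16 = 6.25%, or 6.3% rounded

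**2. Per-hour slope when the total fall is fixed.** Use the same day lengths.
- 16/16.5 − 1 = −3.0%
- 16/17 − 1 = −5.9%

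The two versions err by similar amounts in opposite directions, depending on which model of the decline holds. Neither is neutral to day length.

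**3. The shift in SD units.** Let the change be r × H, with r and H independent, r of mean 1 and SD equal to CV, and H of mean 16 hours and SD s. Then SD(rH) = √(16²·CV² + s² + CV²·s²).
- CV 0.4, s = 1: √(40.96 + 1 + 0.16) = 6.49. Shifts of 0.5 and 1 give 0.08 and 0.15 SD.
- CV 1.0, s = 1: √(256 + 1 + 1) = 16.06. The shifts are 0.03 and 0.06 SD.
- With s = 1.5 the SDs are 6.60 and 16.14, and the rounded shifts are unchanged.

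**4. Agreement between the versions.** Under the same model, corr(rH, r) = 16·CV / SD(rH).
- Lowest: CV 0.4, s = 1.5 gives 6.4/6.60 = 0.97
- Highest: CV 1.0, s = 1 gives 16/16.06 = 0.996

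**5. Precision of a group difference.** This is a simple two-group comparison at one time point, in SD units.
- 20 per arm: 2.024 × √(2/20) = 0.64 SD
- 16 per arm (assumed, if some caregivers give no saliva): 2.042 × √(2/16) = 0.72 SD

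The largest shift against the narrower half-width is 0.15/0.64 = 0.23, under a quarter.

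**6. Individual caregivers.** The versions can rank people differently. With assumed values, a fall of 0.30 µg/dL over 17 hours is 0.0176 per hour, while 0.27 over 14 hours is steeper at 0.0193 per hour. This is variation between people. It biases the group contrast only if day length differs by arm.

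**7. Saliva order.** Table 2 is titled as the assessment plan, and salivary collection is one of its rows, at T1, T2 and T3. The Outcome Measures section sends the reader to that table. Read with the Design section, saliva is part of the baseline assessment that precedes randomisation and part of the final T3 assessment that precedes the offer of the kit.

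**The case for a change.** The strongest argument is that this is the one cortisol measure with a directional hypothesis, so its definition should be beyond doubt, and a sentence would make it so. The diary times will be on file, and the plan does not say what they are for. The summary measures also enter the exploratory Aim 2 models as predictors, so any ambiguity carries over. Randomisation balances waking-day length in expectation at T1 but cannot prevent a difference arising by T2. The cited method does not clearly settle the matter: by position it attaches to intraindividual variability, and the plan's own gloss still describes a plain change.

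It stands that the use of diary times is unstated, and a report should give the unit of the slope and say how the two days were combined. It does not stand that the hypothesised measure is undefined. Read literally, the plan commits to the difference score, so an analyst who switched to another version after seeing the data would be departing from it. The sleep mechanism is possible but not shown: sleep is one of three topics in one of eight modules, module use is guided by preference, and caregivers may opt out.

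On the saliva order, the phrase "for two consecutive days following T1, T2, and T3" is somewhat loose, and the Human Subjects section lists assessment settings without mentioning home saliva collection. That looseness does not outweigh the explicit listing in Table 2. The T1 return route, "participants will return their samples in person at the radiation clinic (T1", does not by itself fix the order either way.

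**Conclusion.** No change is needed. The difference score is a valid, computable summary, and following the plan as written gives a sound preliminary estimate. A per-hour slope would replace one summary that depends on day length with another. It would also make the main analysis rely on self-recorded times, so caregivers without usable times on either day would drop out of an already small sample.

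The possible distortion of the T2 contrast is about 0.03 to 0.15 SD, against a half-width of 0.64 to 0.72 SD. This rests on an assumed 16-hour day, an arm difference of 0.5 to 1 hour, a between-caregiver CV of 0.4 to 1.0 and a day-length SD of 1 to 1.5 hours. None of these comes from the documents. Aim 3 is described as preliminary, and the sample size rests on Aim 1 feasibility, so no confirmatory claim depends on the choice. An analyst can report the per-hour version alongside from data already collected.

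The saliva-order worry is met by the natural reading of Table 2 with the Design section. Its size cannot be derived, and holding back the kit for saliva participants alone would make intervention start depend on saliva eligibility.

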Intervention Delivery and Participation: *Prepare to Care* kit materials are offered in a blended delivery format. To maximize intervention engagement, in addition to the intervention kit, modules are also accessible on a study website and iPads linking directly to the website will be available for use at the RT clinic. Modules 3-8 are designed to take 30- 45 minutes each, and each module does not have to be completed in one sitting; caregivers are instructed to complete at least one module per week and re-visit previous modules as needed. Each week, caregivers will complete a needs assessment with the interventionist to help direct them to relevant modules. However, if new challenges present during the week, caregivers are encouraged to use other pertinent modules. This preference-based approach empowers caregivers to build skills to address current challenges. The workbook will include a time log for caregivers to record the date, modules utilized, and times for starting and ending each module. Waitlist control caregivers will not meet with the study interventionist when provided with the intervention.

Interactions with Interventionist: During weekly interventionist sessions (estimated to take 10-30 min), the interventionist will complete needs assessments, as discussed above, and inquire about modules used the prior week, assist in overcoming potential barriers to participation, and assist with incomplete activities, if desired. These sessions will occur weekly at the RT clinic when caregivers typically accompany the patient, capitalizing on the existing infrastructure for treatment schedules and thereby reducing participant burden. When necessary, sessions can also be completed via telephone. The interventionist will also send weekly email and/or text reminders each Wednesday to engage with caregivers and support adherence. The interventionist has extensive experience interacting with participants in psychosocial/ behavioral research studies and will be trained in intervention content. Waitlist control caregivers will not meet with the study interventionist when provided with the intervention.

Outcome Measure(s)

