Intermediate Outcomes		
Self-efficacy in coping with cancer Caregiver Inventory (CI)[47]	T1; T2; T3	21-item instrument assessing caregivers' perceived self-efficacy for coping with cancer (managing medical information, caring for care recipient, caring for oneself, managing difficult interactions/emotions); demonstrated validity and reliability.
Self-efficacy in PMR	T1; T2; T3	3-item instrument developed for study to evaluate self-efficacy in PMR.
Outcome Variables		
(CES-D) [48]	T1; T2; T3	20-item instrument how often over the past week they experienced symptoms associated with depression, such as restless sleep, poor appetite, and feeling lonely. The CESD has been widely used in caregiver populations.
(PROMIS Emotional Distress Anxiety Short Form- 8a)[49]	T1; T2; T3	Brief 8-item assessment of anxiety over the past week.
Caregiver burden • Caregiver Reaction Assessment (CRA) [50]	T1; T2; T3	24-item instrument assessing positive and negative aspects of caregiving (esteem, lack of family support, finances, schedule, and health). The CRA has been tested in cancer caregivers; demonstrated validity and reliability [50, 51].
QOL • Caregiver Quality of Life Index-Cancer (Cqol-Canc) [52]	T1; T2; T3	35-item instrument assessing dimensions of caregiver QOL (burden, disruptiveness, positive adaptation, financial concerns). The Cqol-Canc has demonstrated validity and reliability [51, 52].
Aim 3		
Salivary Cortisol Collection (for eligible caregivers only)	T1; T2; T3	Collected three times a day (at awakening, 30 minutes post-awakening, and bedtime) for two consecutive days following T1, T2, and T3. Saliva samples are collected by placing a cotton roll under the tongue for approximately 1-2 minutes which is subsequently stored in a plastic tube and refrigerated.
Aim 4		
Modules Utilized (intervention caregivers only)	Study duration	Frequency of intervention modules utilized; retrieved from caregiver logs
Interventionist notes	Study duration	Process notes regarding intervention implementation

Analytical Plan

The analyses will provide quantitative data on participation, retention, and accrual, and estimates of the effect size of the intervention for intermediate and outcome variables. This information, along with ratings of acceptability and qualitative analyses, will allow us to refine the protocol for a larger study.

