We anticipate that participants who more fully utilize the modules may derive a greater benefit than those who do not. We will include utilization as an interaction term in the mixed effect model to assess this hypothesis in an exploratory analysis. This information will help us to refine the protocol, but will not be fully powered to quantify effects. Quantitative and qualitative findings will be synthesized, along with interventionist implementation notes, and included in a final report. The report will be used to determine potential refinement in the recruitment process, content of intervention materials, delivery of intervention components, and email/text reminders. The report will be presented to advisory panel members who will participate in making final decisions for refinement.

Human Subjects Protection

All team investigators have completed their institution's courses for Protection of Human Research Subjects and will maintain up to date certification throughout the study period.

Human Subject Involvement and Characteristics.

Caregiver involvement. This study will enroll 40 head and neck cancer (HNC) caregivers recruited from the outpatient radiation clinics at the Comprehensive Cancer Center of Wake Forest University (CCCWFU) and the Lexington Medical Center or by mail. Caregivers will be recruited before or at the start of patient RT and participation will end 6 weeks after patients complete RT. Caregivers will participate in either an intervention group that provides psycho-education and teach stress management skills during the patient's radiotherapy (RT) treatment or a waitlist control group who will receive the intervention at the end of the study, without interventionist support. The intervention (or kit) includes an introduction to the kit with a DVD, a binder including eight workbook modules offered in hard copy, and a CD with audio instructions to facilitate progressive muscle relaxation (PMR) training (included in module 8). An interventionist will meet with caregivers weekly for approximately 10-30 min. Caregivers will complete assessments at the start of the patient's RT (T1), at the conclusion of RT (T2), and 6-weeks post-RT (T3). All quantitative data will be in the form of self-report and qualitative data (intervention group only) will be collected via semi-structured interviews. All assessments will take place while at the RT clinic, by Redcap, by mail, or by phone.

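### Does Aim 4 have to name what module utilization interacts with, and whether its main effect is in the model?

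*Combined protocol and SAP*

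**What the plan says.** The Analytical Plan, Aim 4, expects that "participants who more fully utilize the modules may derive a greater benefit than those who do not". To examine this it says: "We will include utilization as an interaction term in the mixed effect model to assess this hypothesis in an exploratory analysis". It adds that the analysis lacks full power. The results join the qualitative findings and the interventionist's notes in a report for an advisory panel.

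The model referred to is the one under Aims 2a and 2b: "a mixed effects model with a random subject effect and time (T1,T2,T3), group, and a group by time interaction", used there to model change across the three visits. The group comparisons are specified separately: "We will use linear contrasts to compare the intervention to the control group at T1, T2, and T3".

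Table 2 describes the utilization measure as "Frequency of intervention modules utilized; retrieved from caregiver logs". It is collected in intervention caregivers only, over the whole study. Under Intervention Delivery and Participation, "caregivers are instructed to complete at least one module per week and re-visit previous modules as needed", and the log records dates and times. Under Design, "After baseline assessment, caregivers will be randomized at the time of registration", and waitlist caregivers are offered the materials only after T3.

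**The concern.** An interaction needs a partner, and the Aim 2 model offers three: time, group, and group-by-time. The text picks none and is silent on the main effect. Three different models can be fitted:

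- **A.** Utilization plus utilization-by-time: the slope of change from T1 on use.
- **B.** Utilization-by-time without the main effect: this forces heavier and lighter users to be equal at T1.
- **C.** Utilization-by-group: the slope of the T1, T2 and T3 average on use, although T1 comes before randomization and so before any use.

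The score is open as well. With re-visits allowed, a frequency can mean distinct modules (at most eight) or number of uses.

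At stake is the answer to the Aim 4 hypothesis. C would shrink a real gain. If heavier users start out worse, A and C can have opposite signs in the same data. An analyst who had seen the results could then choose between them.

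**Working it through.** The documents give no figure for this analysis, so there is none to reproduce. Taken from them: 20 caregivers per arm, three visits, utilization in the intervention arm only, no control use before T3, T1 before randomization. Assumed: unit-variance scores (higher is worse), use scaled to SD 1, equal between-visit correlation rho, controls coded 0, complete data.

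**Which models exist.** The base model has 6 fixed-effect columns: intercept, group, T2, T3, group×T2, group×T3.

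- A adds utilization, utilization×T2 and utilization×T3: 9 columns, rank 9.
- B adds only the last two: 8 columns, rank 8.
- C adds utilization×group: 7 columns, rank 7. With controls at 0 this column is identical to utilization itself. Entering both gives 8 columns but rank 7.
- The full three-way model has 12 columns and rank 9, so it reduces to A.

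C is therefore a main-effect model and not a working interaction. B drops a main effect that is ordinarily kept with its interaction. A is the standard form.

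**What each estimates.** Let b1, b2, b3 be the slopes of the score on use at T1, T2, T3. At T2, A gives b2 − b1 and B gives b2 − rho×b1. C gives (b1 + b2 + b3)/3.

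| Assumed case | A | B | C |
|---|---|---|---|
| Gain 0.30 at T2 and T3, no confounding: slopes 0, −0.30, −0.30 | −0.30 | −0.30 | −0.60/3 = −0.20 |
| Gain 0.30 at T2 only: slopes 0, −0.30, 0 | −0.30 | −0.30 | −0.30/3 = −0.10 |
| No effect, use follows T1 need (r = 0.4, rho = 0.6): slopes 0.40, 0.24, 0.24 | −0.16 | 0.00 | 0.88/3 = +0.29 |
| Same with r = −0.4 | +0.16 | 0.00 | −0.29 |
| No effect, use follows later need (rho = 0.6): slopes 0.40, 0.50, 0.50 | +0.10 | 0.50 − 0.24 = +0.26 | 1.40/3 = +0.47 |

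Without confounding, A and B agree and C differs from them by 0.10 or 0.20 SD.

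**How often signs conflict.** In simulated trials at r = 0.4 and rho = 0.6, A is negative while C is positive in about 72% (50% to 88% over r 0.2 to 0.6 and rho 0.5 to 0.7). That needs a chance baseline. Under no effect and no confounding, the covariance of b2 − b1 with b1 + b2 + b3 is proportional to (1 + 2rho) − (1 + 2rho) = 0. The two slopes are then uncorrelated, and this pattern occurs by chance in ½ × ½ = 25% of trials; opposite signs in either direction occur in 50%. At r = 0.4, both slopes reach p < 0.05 in opposite directions in only about 3% of trials.

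**Precision.** The mean 95% half-width of the change slope (r = 0.4, rho = 0.6) is about 0.42 SD per SD of use with 20 caregivers and 0.48 with 16. The latter is 0.80 × 20, using the retention figure in the Sample Size section.

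**The case for a change.** The best case for a change is that one sentence would close the gap at no cost. The plan can be exact when it wants to be: under Aim 2 it says the intermediate variable enters as a fixed effect. The result feeds the refinement report, and low power is no reason to leave an estimand unnamed.

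Part of this stands. The text names no partner, the score has two readings, and none of the slopes is a randomized contrast, because weekly needs assessments partly steer use. But the surrounding text points to A, and the other readings require choices that an analyst would not ordinarily make. The striking sign reversals come from assuming that more need leads to more use. The documents give no direction, and the opposite assumption reverses the signs.

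Naming the term would not remove confounding either. Adjusting the T2 slope for T1, (b2 − rho×b1)/(1 − b1²), moves −0.16 to 0.00 if use follows T1 need. If use follows later need, it moves +0.10 to 0.26/0.84 = +0.31. Neither version can be declared right in advance. Counting use only up to T2 would narrow the whole-study measure in Table 2, and the dated log already lets the analyst report either count.

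**Conclusion.** This is missing detail that an analyst fills sensibly, so the plan can stand. Benefit in a model of change means utilization plus utilization-by-time. Fitted that way, it gives a sound exploratory association, to be reported with its interval and read as non-randomized. No stated rule leads to a wrong result.

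The one reading that would mislead, utilization-by-group, shows a T2 and T3 gain at two thirds of its size, but it is only the main effect relabelled. Without confounding the readings differ by 0.10 to 0.20 SD, less than half of the 0.42 to 0.48 SD half-width. No decision threshold hangs on the slope. Feasibility, which drives the sample size, and the Aim 2 contrasts do not use it.

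The rank results depend only on control use being 0. The slopes, sign percentages and half-widths rest on assumed correlations and effects; the slope formulas and rank results also take the data as complete.
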